3 OVERVIEW OF STUDY DESIGN

This study is a cluster-randomized, two-arm controlled trial in primary care settings. A total of 4 primary care clinics in rural Alabama will be randomized to either 1) Receive lifestyle modification alone (DPP) or 2) Receive lifestyle modification with metformin therapy recommendations (DPP-recommendations). The sample will include up to 100 adults with obese (BMI 30-50 kg/m²) patients (4 clinics, 25 patients / clinic).

The primary aim of this trial is to conduct a 12-month randomized control trial (RCT) to determine the feasibility of implementing a peer coach-facilitated DPP delivered by telehealth. The DPP will be compared to DPP with metformin therapy recommendations. The goal of the intervention is to prevent or delay the Type 2 diabetes among rural primary care patients with pre-diabetes and obesity at high risk for developing diabetes. The primary outcomes are body weight and HbA1 results at month 12. The RCT will test feasibility and provide data that will inform design and power for a future study to assess diabetes prevention as the main outcome measure. All participants will receive the lifestyle intervention of the Diabetes Prevention Program (DPP) plus telemonitoring of their body weight using an Ideal Life body weight scale. The DPP is a 12-month intensive lifestyle modification intervention that includes 16 group-based sessions over 6-months and 6 group-based sessions in the remaining 6-months. Consistent with the DPP, content includes fundamental components of evidence-based lifestyle interventions, including recommendations for dietary modification, increased physical activity, and behavioral strategies designed to promote treatment adherence. The current intervention includes two new features, a telemedicine platform and the participation of community health workers. Participants will be partnered with a Community Health Worker (CHW) who will facilitate the delivery of the group-based session delivered by a trained nurse or dietitian joining via the telehealth platform. The CHW will assist participants in setting up the telemonitoring and conduct 16 brief weekly calls and 6 monthly calls over the 12-month intervention.

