4.1 INCLUSION CRITERIA

- Age 19 (the age of adulthood in Alabama) to 65 years
- A1c (A1c) 6.0% to 6.4%
- Body mass index (BMI) 30-50 kg/m²
- Receives care at one of the 4 participating primary care clinics
- Resides in one location at least 5 days each week
- Telephone line or Wi-Fi internet connection or cellular signal in home
- Willing or able to partner with a Community Health Worker
- Willing to attend group sessions

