4.2 EXCLUSION CRITERIA

- Pregnancy or anticipating pregnancy
- Diabetes (A1c $\geq 6.5\%$, and/or chart value of fasting glucose ≥ 126 mg/dl, and/or diabetes medications)
- Unwilling or unable to do any of the following: give informed consent, accept random assignment, allow study staff to visit them at their primary care clinic for two follow-up visits
- Likely to relocate and no longer be seen at primary care clinic in the next 2 years
- Weight loss or gain $\geq 5\%$ of body weight in past 6 months (other than postpartum)
- Prescription weight loss medications within the past 6 months
- Another household member already participating in the study
- Abnormal thyroid status
- eGFR ≤ 60
- not able to ambulate or have end-stage medical conditions with limited life expectancy

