6.1.1 DESCRIPTION OF LIFESTYLE INTERVENTION ARM

All enrolled participants will receive lifestyle modification intervention. Participants will receive Diabetes Prevention Program Curriculum educational materials related to PreventT2 intervention that include evidence-based recommendations for dietary modification, increased moderate-intensity physical activity, and behavioral strategies designed to support these lifestyle changes to promote healthy weight loss to delay or prevent the development of type 2 diabetes.

Program materials were accessed and printed for study use from public sources:

<https://www.cdc.gov/diabetes/prevention/resources/curriculum.html> The CDC Diabetes Prevention Program Curriculum (CDC DPP Curriculum) is based on the curriculum from the Diabetes Prevention Program (DPP) research study supported by the National Institutes of Health, National Institute of Diabetes and Digestive and Kidney Disease (U01-DK48489). All participants will also receive a RM body weight scale, the Ideal Life Body Weight Scale. Participants will be asked to: (1) keep the scale in their bedroom, (2) weigh daily at the same time in light clothing, and (3) view and log their daily weight checks. Study staff will review with participants how to set-up and use the scale. Participants will receive a binder and additional program materials over the course of the 12-month program. Trained health educators will deliver the DPP intervention to all participants on a rolling schedule. The DPP is an evidence-based intensive lifestyle modification program to prevent or delay type 2 diabetes that asks that participants attend 26 group sessions over 12 months. Peer coaches will facilitate the delivery of the DPP. Participants are asked to attend 16 weekly group sessions, 4 bi-monthly sessions, and 6 monthly sessions over the course of 12 months. Group sessions will be held via Zoom.

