6.1.2 DESCRIPTION OF LIFESTYLE INTERVENTION WITH METFORMIN THERAPY RECOMMENDATIONS ARM

Lifestyle intervention program (telehealth + peer coach) with metformin therapy recommendations (DPP-recommendations): Participants will receive the same lifestyle intervention as those in the DPP condition described above. In addition to the lifestyle intervention, they will receive a recommendation for metformin therapy for prevention of type 2 diabetes. Primary care providers at the practices randomized to the DPP-recommendations condition will attend an orientation session and evidence-based materials about low-dose metformin therapy recommendations for patients with pre-diabetes to prevent or delay the onset of type 2 diabetes. At the baseline assessment, study staff will provide participants with the patient education handout on “Understanding Metformin for Pre-diabetes” that details using metformin for prevention of type 2 diabetes. At the same time, the participant’s primary care provider will receive a recommendation to provide their patient with a prescription for Metformin for diabetes prevention. The communication between study staff and PCPs will be developed and

tailored to fit the work flow of each clinic. As described in the inclusion/exclusion criteria, participants without a charted eGFR or an eGFR<60 within the last 6-months will be excluded from the study.

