13 DATA ANALYSIS PLAN

Mixed models will be used to estimate the changes in outcomes by intervention with confidence intervals using practice as a random effect to account for clustering within practices. Secondary models will adjust for baseline values. In 2011, Katula et al. published 12-month results of randomized controlled trial comparing a community-based translation of a DPP lifestyle intervention conducted in a southern sample with usual care. Combined with data generated in our feasibility trial, this relevant study should further help inform our power assessments for a larger RCT. The change values observed in the control group in that project will serve as a reference for expected change in weight without any intervention and will be used to estimate the change due to the intervention.

Handling of Missing Data

Missing data are expected due to dropouts and missed visits. Weight loss is a subject-level variable and missing assessments would influence tests relative to treatment-by-time interactions. The primary analysis described above will employ restricted maximum likelihood using all data. No patients will be deleted from the analysis because of partial data. To assess the sensitivity of results, weight loss will be

analyzed using: 1) all patients irrespective of missing data to perform analysis of variance using mixed effects multi-level models with repeated measures; 2) only patients who have completed all assessment visits and have no missing data, to perform analysis of variance employing mixed effects multi-level models with repeated measures; 3) all patients, irrespective of missing data, to conduct analyses using mixed effects multi-level time trend models with random coefficients to capture individual time trends (does not require complete data across time); and 4) multiple imputation.

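### The outside usual-care weight change can give only a non-randomised benchmark; the plan should label it so and carry its sampling error

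*Combined protocol and SAP*

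**What the plan says.** Section 13 (Data Analysis Plan) first specifies mixed models, with practice as a random effect, for the changes in each arm. It then cites a randomised trial published in 2011, described as "comparing a community-based translation of a DPP lifestyle intervention conducted in a southern sample with usual care". Together with this pilot's data, that trial "should further help inform our power assessments for a larger RCT". The next sentence makes the weight change in that trial's control group the reference for the "expected change in weight without any intervention and will be used to estimate the change due to the intervention".

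The lifestyle programme is given in both arms. Section 6.1.1 states: "All enrolled participants will receive lifestyle modification intervention". Section 6.1.2 says of the metformin-recommendation arm: "Participants will receive the same lifestyle intervention as those in the DPP condition described above". Sections 2.2 and 3 agree. Under sections 3 and 5, what is randomised, across four clinics, is lifestyle modification alone against lifestyle modification plus a metformin recommendation.

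Section 13 gives no value, SD, standard error or sample size for the outside control group, and no method for combining it with this trial's estimates. The precision figures in section 12 and the missing-data methods in section 13 cover this trial's own data only.

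**The concern.** No participant in this trial is allocated to go without the programme, so randomisation cannot supply a weight change attributable to it. Subtracting an outside group's change from the change seen here is a historical-control comparison. Two things are then missing from the plan.

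- **A label.** The sentence describes the result as due to the intervention. It does not say that the contrast is non-randomised and non-concurrent. It also treats the reference as change with no intervention, although the same paragraph says that the outside comparator was usual care.
- **The error of the reference.** The outside mean is itself an estimate. An interval that reflects only this trial's variation would be too narrow.

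Weight is a primary outcome (sections 1.1 and 7), and this would be the only figure said to measure what the lifestyle programme did to it. A reader could take it as a causal effect of the adapted DPP, or the larger trial could be sized on an effect whose uncertainty is understated.

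**Working it through.** **Step 1: which contrast is randomised.** Sections 3, 6.1.1 and 6.1.2 put the lifestyle programme in both arms. The arm difference therefore estimates the effect of adding the metformin recommendation. A lifestyle effect on weight needs a group without the programme, and the only one named is the outside usual-care group in section 13.

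**Step 2: the plan's own precision (section 12).** Inputs: 50 per arm, or 40 after 20% attrition; two clinics per arm; ICC 0.01; design factor D = 1 + ICC × (N − 1), with N patients per clinic.

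- No attrition: D = 1 + 0.01 × 24 = 1.24; effective n = 50/1.24 = 40.3 (the plan says 40).
- With attrition: D = 1 + 0.01 × 19 = 1.19; effective n = 40/1.19 = 33.6 (the plan says 33).

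The half-width for one arm's mean change, in SD units, is 1.96/√n:

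- n = 40.3: SE = 0.157, half-width 0.31.
- n = 33.6: SE = 0.172, half-width 0.34.

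The plan states 0.28 to 0.35. The upper value agrees with effective n = 33 (0.34 with a normal quantile, 0.35 with a t quantile). The lower value matches the unadjusted n = 50 (1.96/√50 = 0.277), not the effective n of 40 (0.31). That is a separate matter. The calculation below uses 0.31 and 0.34, the half-widths that follow from the plan's design factors.

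**Step 3: carry the outside group's error.** Its size m is not in the documents. I assume m = 50 to 300, the same SD as here, no clustering in the outside group, and a normal approximation.

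- Half-width with the error carried = 1.96 × √(1/n + 1/m).
- Coverage of a nominal 95% interval that treats the outside value as fixed = 2Φ(1.96/√(1 + n/m)) − 1.

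| Assumed m | Half-width, n = 40.3 | Coverage if fixed | Half-width, n = 33.6 | Coverage if fixed |
|---|---|---|---|---|
| Treated as fixed | 0.31 | n/a | 0.34 | n/a |
| 50 | 0.41 | 86% | 0.44 | 87% |
| 100 | 0.37 | 90% | 0.39 | 91% |
| 150 | 0.35 | 92% | 0.37 | 92% |
| 300 | 0.33 | 93% | 0.36 | 94% |

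For example, n = 33.6 and m = 50 gives 1.96 × √(0.02975 + 0.02000) = 0.437.

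The range is therefore 0.33 to 0.44 SD with the error carried, against 0.31 to 0.34 SD without it. Using t quantiles and the rounded n of 40 and 33 gives 0.34 to 0.46 SD against 0.32 to 0.35 SD.

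**Step 4: what this leaves out.** Carrying the standard error does nothing about bias. If weight change under usual care differed between the two populations by d SD, the benchmark would shift by d SD. The documents give no value for d. This trial restricts entry by A1c and BMI (section 4.1) and by recent weight stability (section 4.2); section 13 does not say how the outside controls were selected.

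**The case against.** The strongest reply is that the sentence is about planning. It follows directly on one about power for a larger trial, and the pilot purpose runs through sections 1.1, 3 and 12. A power calculation needs an assumed effect, and subtracting an expected usual-care change from an observed change is a normal way to get one. No endpoint, hypothesis test or progression rule uses the contrast. The paragraph also says openly that the reference comes from another published trial with a usual-care comparator.

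Much of this stands. Planning may be all that is meant, and an attentive reader can see that the reference is external. But the clause sits in the analysis plan, speaks of estimating change due to the intervention, and does not limit itself to planning. Even for planning, the reference's error should pass into the assumed effect.

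The size of the problem can also be questioned. The outside sample size is an assumption, and at 300 the half-width grows by only about 0.02 SD. That stands, which is why the range is shown. With only two clinics per arm, uncertainty about clinic-level variance could exceed the term being added. That also stands; these figures isolate one component and are not a full interval.

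Two stronger readings are tempting. A reader might infer that the benchmark is biased because the populations differ. The documents show no actual difference, only that selection of the outside controls is not described. A reader might also infer that the main analysis is compromised, or that within-arm changes must be downgraded to descriptive. Neither follows: the mixed models use this trial's data alone, and estimating change by arm with confidence intervals is a legitimate pilot aim.

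**Conclusion.** The point holds as one of labelling and error. Any lifestyle effect on weight derived from the outside control group is a non-randomised, non-concurrent benchmark against usual care, and section 13 neither says so nor provides for the reference's sampling error. That conclusion rests on the design and needs no assumed number.

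The amount of widening is illustrative, because it depends on the assumed outside sample size, equal SDs and the normal approximation. Ignoring the outside error costs little if that group was large and is material if it was about the size of one arm here. Bias from population differences would come on top, by an amount that the documents do not allow one to determine.

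The scope is limited to weight. The comparison between the randomised arms is untouched. The change should be made, but it is not a design flaw.

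**What to change.** In section 13, replace the run "expected change in weight without any intervention and will be used to estimate the change due to the intervention" with:

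*expected change in weight under usual care and will be used as a non-randomised external benchmark, for planning the larger RCT. Any difference between the within-arm change and this benchmark will be reported with SE = √(SE_arm² + SE_outside²), with a statement of how the two populations differ, and will not be described as a randomised effect of the lifestyle programme.*

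The statement on populations should cover at least the entry limits on A1c, BMI and recent weight change.

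The cost is a sentence or two. The main mixed-model analysis, the data collection and the participants' schedule do not change. The downside is a wider interval around the benchmark difference and no causal claim for the lifestyle programme from this pilot.

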Multiple imputation will be employed to perform statistical inferences that properly account for statistical uncertainty due to missingness. Rubin's multiple imputation procedure replaces each missing value with a set of plausible values that represent the uncertainty about the appropriate value to impute.⁸⁴ Missing values are imputed by drawing random samples, and the process is replicated to provide K data sets with pseudo-complete data. Estimates and corresponding confidence intervals will be plotted against K to determine the optimal K to use in subsequent sensitivity analyses. Mean weight loss is estimated for each data set, and the multiple imputation estimator is the average of the individual estimates. The variance of the estimator is estimated from between- and within-imputation variability. The SAS® procedure PROC MI provides four relevant options for imputation models and will be used in quantifying uncertainty due to missing data.

Statistical summaries will be compiled on the number of patients overall and by arm and who completed study per protocol, did not complete study per protocol, and reasons for not completing. Patient characteristics (age, sex, race, BMI) will be summarized similarly. Multi-level logistic regression will be used to investigate the significance of correlates of failure to complete the study per protocol.

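### The planned missing-data analyses of weight test model form and completer restriction, but none tests a departure from missing at random such as weight regain in dropouts

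*Combined protocol and SAP*

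**What the plan says.** Section 13 (Handling of Missing Data) opens by accepting that "Missing data are expected due to dropouts and missed visits". Section 12 allows for 20% attrition, from 50 to 40 participants per arm.

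For the main result, "The primary analysis described above will employ restricted maximum likelihood using all data". Four sensitivity analyses of weight loss follow:

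1. "all patients irrespective of missing data to perform analysis of variance using mixed effects multi-level models with repeated measures";
2. the same type of model on "only patients who have completed all assessment visits and have no missing data";
3. for all patients, "mixed effects multi-level time trend models with random coefficients to capture individual time trends";
4. multiple imputation.

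On the fourth, the section says "Multiple imputation will be employed to perform statistical inferences that properly account for statistical uncertainty due to missingness", and describes the standard procedure: "Missing values are imputed by drawing random samples, and the process is replicated to provide K data sets with pseudo-complete data". The imputation model is left open; the SAS procedure "provides four relevant options for imputation models and will be used in quantifying uncertainty due to missing data". Reasons for non-completion will be tabulated by arm and its correlates modelled.

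The same section says that an external study's control group will stand for weight change without intervention, and that the change due to the intervention will be estimated against it.

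**The concern.** A sensitivity set is most useful when it varies the assumption most in doubt. In a weight programme that assumption is that people who leave would have had the same month-12 weight as comparable people who stay. Dropouts may instead regain weight after their last visit, and no analysis in Section 13 represents this. There is no shift of imputed values, no return-to-baseline or reference-based rule, no pattern-mixture model and no joint model for dropout.

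Clinic weight is measured only at baseline, month 6 and month 12 (Section 7). A participant who leaves before month 6 contributes a baseline weight only, and a missing-at-random method credits that person with roughly the loss seen in those who stayed.

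What is at stake is the estimate itself. Section 12 describes a pilot whose product is the precision of estimated changes for planning later studies. If the planned analyses agree, the report could present the weight change as robust to missing data without having varied this assumption.

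**Working it through.** **Inputs from the documents.** Enrolment of 50 per arm, 20% attrition, ICC 0.01, effective sizes of 40 and 33, and half-widths of 0.28 to 0.35 SD for change within an arm (Section 12).

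**Assumed inputs, not in the documents.** Missing-at-random mean loss of 4% (range 3% to 5%), SD of percent change 6 points, and unequal attrition of 10% and 30%.

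**1. The plan's own figures.**
- Design factor: 1 + 0.01 × 24 = 1.24, and 50/1.24 = 40.3. With attrition: 1 + 0.01 × 19 = 1.19, and 40/1.19 = 33.6. Both agree with the stated 40 and 33.
- The t-based half-width at 33.6 is 0.35 SD, as stated. At 40.3 it is 0.32 (normal: 0.31). The stated 0.28 matches 50 participants without clustering (normal 0.277, t 0.284). This is a side point and does not alter the comparison below.

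**2. What each analysis assumes.**
- Primary, 1 and 3: likelihood-based mixed models with no dropout component described, so valid under missing at random.
- 2: completers only, a stronger assumption.
- 4: Rubin's imputation with no shift or reference rule stated, so missing at random as described.

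**3. Effect of regain on one arm's mean.** Shift = missing fraction × difference between dropouts' actual and predicted change.
- Return to baseline: 0.20 × 3, 4, 5 = 0.6, 0.8, 1.0 points.
- At SD 6: 0.6/6 = 0.10, 0.8/6 = 0.13, 1.0/6 = 0.17 SD.
- Without fixing the SD: a delta of 0.25, 0.50, 0.75 or 1.00 SD shifts the mean by 0.05, 0.10, 0.15 or 0.20 SD. For a 4-point loss these deltas correspond to SDs from 4/0.25 = 16 points down to 4/1.00 = 4 points.
- To move the mean by a full stated half-width, delta must be 0.28/0.20 = 1.4 to 0.35/0.20 = 1.75 SD.

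**4. Effect on the arm difference.**
- Equal attrition and equal regain: (0.20 − 0.20) × 4 = 0.
- Attrition of 10% and 30%: (0.30 − 0.10) × 4 = 0.8 points, or 0.13 SD (0.10 to 0.17 over losses of 3% to 5%).
- Half-width of the difference: 1.96 × √(2/40.3) = 0.44 and 1.96 × √(2/33.6) = 0.48 SD.

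**5. Can the planned analyses agree and still be wrong?** A large simulation (400,000 subjects) assumed a correlation of 0.7 between month-6 and month-12 change, an intended mean loss of 0.8 SD, and dropouts back at baseline on average at month 12. Mean loss in SD:

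| Dropout mechanism | Completers | Missing at random | Truth |
|---|---|---|---|
| 20% at random | 0.80 | 0.80 | 0.64 |
| About 21%, more likely after poor month-6 loss | 0.92 | 0.80 | 0.73 |

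In the first row the two estimates agree and both overstate the loss by 0.16 SD. In the second they diverge, and the missing-at-random error falls to 0.07 SD. With an intended loss of 0.4 SD under the second mechanism, the missing-at-random estimate slightly understates the loss, by 0.02 SD.

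**6. Consequence for planning (illustration).** If the external reference change is taken as zero, 20% returning to baseline leaves 80% of the estimated effect, and a sample size based on it would need multiplying by 1/0.80² = 1.56. If the reference group lost 1 point, the factor is ((4 − 1)/(3.2 − 1))² = 1.86.

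**The case against.** The documents never name missing at random. It is inferred from the methods and, for multiple imputation, from the absence of any shift rule while the imputation model is still open. That is correct, and it is why the point is limited to the analyses as described.

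A reader might infer that the set says nothing about robustness, or that all the analyses must overstate weight loss together. The documents do not support either reading. The set does examine model form and restriction to completers, and the simulation shows completers and missing-at-random methods separating when dropout follows poor month-6 loss. Agreement fails to reassure; it is not proof of bias.

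A reader might also infer that the arm comparison is in danger. Both arms receive the same lifestyle programme, and participants who do not tolerate metformin are to be followed for the full 12 months (Sections 10.1 and 11.1.1.3), which guards against one source of unequal loss. The 10% and 30% split is an assumption. Even then the shift is well inside the interval for the difference. With only two clinics per arm, an interval on 2 degrees of freedom would be wider still: 4.30 × √(2/33.6) = 1.05 SD.

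The size for one arm is also moderate, since a delta of 1 SD moves the mean by 0.20 SD, inside the stated half-width. This stands and limits the severity. It does not close the gap: a confidence interval describes sampling error and does not cover this bias.

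Finally, home-scale weights are recorded automatically (Section 10.1, Sources of Materials) and charts will be reviewed for all participants (Section 7). These could supply real weights for some dropouts, but Section 13 does not commit to using them.

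**Conclusion.** The concern holds for departures from missing at random. The primary analysis and sensitivity analyses 1, 3 and 4 share that assumption as described, analysis 2 is restricted to completers, and no planned analysis varies what dropouts weigh at month 12.

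The size is moderate: 0.8 points (0.6 to 1.0) off an arm's mean loss at 20% attrition, about 0.13 SD. This rests on the assumed 4% loss (3% to 5%), the assumed SD of 6 points and full return to baseline. The within-arm change set against the external control group is where it matters most, because regain in this trial's dropouts does not cancel there. In the arm difference it cancels when attrition and regain are equal, and stays small relative to the interval under the unequal case examined.

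This is a cheap improvement to an estimation pilot and does not invalidate the planned analyses. Nor does it make analysis 1 a duplicate to be deleted, since Section 13 does not state that the primary model is a repeated-measures one.

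**What to change.** Keep the four planned analyses and add one prespecified delta-adjusted multiple imputation on the PROC MI data sets already planned:

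- State which imputation model produces those data sets.
- Add 0 to 100% of the observed mean loss back to the imputed month-12 weights, by arm, in equal and unequal combinations. The 100% end represents return to baseline, on average, when the imputed mean loss matches the observed one.
- Report the arm means, the change relative to the external reference and the arm difference, each with confidence intervals across the range. A tipping point is not needed, because the pilot sets no decision threshold.
- Where home-scale or chart weights exist for dropouts, use them to inform delta, and say so in Section 13.

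The cost is a few lines of text and code, one more table and a less favourable lower bound on weight loss.
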